3.7 Compliance and Reconciliation

Site personnel will assess dosing regimen compliance and drug reconciliation in an ongoing manner. At each subject visit, subject compliance will be evaluated and documented, including calculating the expected amount of consumed drug given the regimen and amount of time between visits. This figure will be compared with the amount dispensed minus the amount the subject returned. Site personnel will question the subject regarding any discrepancies in these amounts and document the explanation.

299 Chapter 4 Study Screening

300 **4.1 Participant Recruitment and Enrollment**

Approximately five subjects will be enrolled into the Pilot Study. The Pilot participants will complete use the Basal-IQ Technology with Empagliflozin for 1-3 weeks. They will then participate in a 36-48 hour hotel admission where they will use the Control-IQ System with the Empagliflozin. The safety data from this admission will be presented to the DSMB for review prior to proceeding to the Main Study.

Pilot participants may enroll the Main Study. The study physician may request repeat laboratory
 values if values are greater than 6 weeks from Pilot screening laboratory values. A current
 urine/blood pregnancy test will be required prior to enrolling into the Main Study.

Enrollment in the Main Study will proceed with the goal of completing approximately 40 subjects,
subjects in each group. Subjects will initially be randomized to Empagliflozin use or NO
Empagliflozin use during the study. They will then be randomized to which type of insulin pump

- 312 will be used first.
- 313 Up to 60 participants may sign the consent form.

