- 429 7. Screening Labs – A historical laboratory results within 2 weeks of the screening appointment may be used 430 a. Hemoglobin A1c 431 432 b. Comprehensive Metabolic Panel c. Thyroid functioning test 433 434 d. Urine or serum pregnancy test for all women of childbearing potential 435 Screening procedures will last approximately 2 hours. Once all results of the screening 436 evaluations are available, a decision will be made to determine the participant's eligibility for the 437 study or if one or more part of the screening will have to be repeated. If at the first screening or 438 repeat screening an exclusionary condition is identified, the participant will be excluded from
- participation with follow up and referred to their primary care physician as needed. The study
 physician may elect to rescreen participants and collect additional laboratory values if their
- 441 clinical situation changes. The study physician has the discretion to exclude a study participant if
- 442 concerned about their safety in this trial.

443 **Chapter 5 Randomization Visit**

444 Once eligibility is met, the participant may continue with randomization at the conclusion of the 445 screening appointment. Screening failures and study dropout participants may be replaced.

446 **5.1 Pilot Participants**

447 Participants will not be randomized in the Pilot Study.

448 **5.2 Main Study Participants**

- 449 Approximately 40 participants will be randomized to using Empagliflozin 5 mg per day or not 450 using the medication. Participants will then be randomized to the order of the insulin pump.
- 451 With Empagliflozin:
- 452 Group 1: CiQ x 4 weeks (CiQ-EMPA) then Basal-IQ x 2 weeks (BiQ-EMPA)
- 453 Group 2: Basal-IQ x 2 weeks (BiQ-EMPA) then CiQ x 4 weeks (CiQ-EMPA)
- 454 Without Empagliflozin:
- 455 Group 3: CiQ x 4 weeks (CiQ-NO EMPA) then Basal-IQ x 2 weeks (BiQ-NO EMPA)
- 456 Group 4: Basal-IQ x 2 weeks (BiQ-NO EMPA) then CiQ x 4 weeks (CiQ-NO EMPA)
- 457 Equipment training will be initiated after randomization.

458 Chapter 6 Study Equipment Training

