668 The DSMB may recommend modifications to individual stopping rules if additional safety 669 concerns arise during from their continuing reviews of the study data.

The hotel admission will not be repeated unless required by the Data Safety Monitoring Board(DSMB).

672 **8.3 DSMB Main Study Safety Data Review**

A Data and Safety Monitoring Board (DSMB) will review compiled safety data after the completion of 10 Main Study participants. As a safety measure, the Board will review if the rate of mild ketosis greater than 40% (B-OH-B level > 0.6 mmol), 20% significant ketosis (B-OH-B > 1.5 mmol) and more than 5% DKA (B-OH-B > 3 mmol) to be considered significant to stop the study.

677 A Data and Safety Monitoring Board (DSMB) will review compiled safety data after 10 participants 678 complete 4 weeks of the Main Study. Absence of serious adverse events related to Empaglifozin, 679 the participants will continue with study participation pending DSMB review. The DSMB will 680 review compiled safety data after 10 participants complete the trial. In addition, the DSMB will 681 review all DKA and severe hypoglycemia irrespective of relatedness to study device use, study 682 drug, and all serious events (including UADEs) related to study device use at the time of 683 occurrence. The DSMB also will be informed of any ADEs not meeting criteria for a UADE if the 684 Study PI requests the DSMB review. The DSMB can request modifications to the study protocol 685 or suspension or outright stoppage of the study if deemed necessary based on the totality of 686 safety data available.

687 Chapter 9 Main Study

After DSMB review and approval of the hotel admission safety data, Main Study participants will
 be screened, randomized and trained on the study equipment. Pilot participants may be enrolled
 in the Main Study. Screening and consenting of the Main Study participants may be concurrent
 to the DSMB review. Virtual study visits may take the place of in-person study visits.

692 **9.1 Empagliflozin Treatment Group**

693 **9.1.1 Run-In Phase**

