694 Participants will be asked to record two days of baseline ketone values before initiating the use 695 of the study drug. Participant will then be directed to use the study CGM with Empagliflozin for 696 1-2 weeks. Proceeding to the pump treatment is dependent upon the participant's tolerance to 697 the medication. The study physician may elect to provide the participant additional time in the 698 event of medication side effects.

699 Participants will be instructed on the Glycemic Treatment Guidelines with special focus upon700 CGM readings (section 10.3) and Hyperglycemic Management (section 10.5).

- 701 Participant will meet the following criteria to continue study participation:
- 702 o Adherence to study protocol
- Ketone testing at least 2 times daily, preferably 4 times, with monitored values not
 greater than 0.6/mmol on at least two successive occasions (first measurement should be
 obtained upon waking in a fasting state)
- No adverse events relating to perineal infections, symptomatic postural hypotension, no
 evidence of significant hypoglycemia (< 54 mg/dl) or any other listed adverse effects of
 medication.

709 **9.2 Insulin Pump Training Visit**

Participants will receive pump training dependent upon the randomization group (i.e. Control-IQ
pump for 4 weeks then Basal-IQ pump for 2 weeks.) Training provided is described in Section
6.5.

713 **9.3 Optimization of Insulin Pump Settings**

- 714 Data driven optimization of pump settings can occur any time during the study, particularly if the
- study participant contacts the study physician due to concerns about their pump settings due to
- 716 recurring hypo- or hyperglycemia.

While initiating and maintaining Empagliflozin therapy, the study physician will carefully monitorinsulin dose reductions, especially basal insulin decreases.

719 9.4 Check-In Visits

All participants will be contacted by the study team in the week following the Run-In Phase and the Basal-IQ Pump Training Visits to address issues relating to the study equipment and side effect of the Empagliflozin if randomized to the treatment group. Two check-in visits will occur after the Control-IQ Training Visit. Extra contact with subjects will occur as needed.

724 9.5 Study Device Download

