- 819 mmol/L, participants will be advised to stop the drug and then recheck ketones in 3-4 hours.
- 820 Participants may restart the use of Empagliflozin after the ketone measurement is <0.6 mmol/L.
- 821 All ketosis events should be recorded and evaluated in participants who are taking the study
- 822 drug.
- 823 Experimental participants will be advised to check ketones if symptoms consistent with
- 824 ketoacidosis occur even if blood glucose is not elevated.
- 825 Experimental participants will be instructed on the proper use of the STICH Protocol:
- 826 **ST**op drug,
- 827 Inject bolus insulin (1.5 times the usual correction bolus)
- 828 **C**onsume 30 grams of carbohydrate
- 829 Hydrate with up to 500 ml of water

	Blood Ketone (BHB) Level	Pomodial Actions				
	<0.6 mmol/L (normal)	Remedial Actions No action needed				
	0.6-1.5 mmol/L (ketonemia)	 Treat as follows or per clinician instructions: Ingest 30-60g rapidly absorbed carbohydrates and maintain fluid consumption (200-500 mL) every 1-2 hours Administer rapid-acting insulin based on carbohydrate intake every 1-2 hours Check blood ketones (every 2-4 h) until resolution Check blood glucose frequently to avoid hyperglycemia and hypoglycemia 				
		Seek medical attention if levels persist and symptoms presen				
		Follow treatment recommendations listed above Consider seeking immediate medical attention Seek immediate medical attention ^{19 [11]} will be advised to measure ketones in the event of the followin				
	symptoms/events:					
3	Malaise					
	 Fatigue 					
	-					
5	• Nausea, or vomiting.					
5	Nausea, or vomiting.Infection					
5 5 7	Nausea, or vomiting.InfectionInjury					
5 5 7 8	 Nausea, or vomiting. Infection Injury Occlusion of infusion can 	nula				
4 5 7 8 9	 Nausea, or vomiting. Infection Injury Occlusion of infusion can Pump malfunction 	nula				
5 6 7 8	 Nausea, or vomiting. Infection Injury Occlusion of infusion can 	nula				

Control participants will be advised to measure and document ketone levels each morning.
Experimental Participants will also be instructed on the importance of prompt treatment of
symptoms as recommended in the STICH Protocol.

846 **Chapter 11 Testing Procedures**

847 **11.1 Laboratory / Point of Care Testing**

848 **11.1.1 HbA1c**

- A blood sample will be obtained at screening to obtain a baseline hemoglobin A1c level. Blood
- test may be obtained within 2 weeks prior to enrollment may be used for eligibility purposes.

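### Run-in criteria applied after randomisation, and only to the Empagliflozin arm, end participation for those who fail; once anyone fails, Objectives 1, 3 and 4 are no longer intention-to-treat

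*Combined protocol and SAP*

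**What the plan says.** **Order of events.** In section 4.1, "Subjects will initially be randomized to Empagliflozin use or NO" Empagliflozin, and pump order is randomised next. Chapter 5 says that once eligibility is met, "the participant may continue with randomization at the conclusion of the" screening appointment. Chapter 9 has Main Study participants "be screened, randomized and trained on the study equipment". Objective 2 in 15.1 contrasts the drug and no-drug groups on the baseline CGM, which is possible only if the drug has already been allocated.

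**The run-in.** Section 9.1 covers the Empagliflozin group only. Section 9.1.1 gives 1-2 weeks of study CGM on drug and adds: "Proceeding to the pump treatment is dependent upon the" participant's tolerance of it. It then states "Participant will meet the following criteria to continue study participation" and lists adherence, a ketone criterion (0.6 mmol/L, two successive readings), no perineal infection or postural hypotension, and no "evidence of significant hypoglycemia (< 54 mg/dl) or any other listed adverse effects of" the medication. The physician may allow more time for side effects. Section 15.1 gives all four groups a 1-2 week CGM baseline, but no section sets continuation criteria for Groups 3 and 4.

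**After a failure.** Section 13.6 provides adverse-event follow-up. No section plans CGM during the pump weeks. Section 14.2 leaves it to the study team whether a withdrawn participant's data are used. Chapter 5 adds: "Screening failures and study dropout participants may be replaced".

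**The analysis.** Section 15.1 declares ITT by initial randomisation but includes only randomised participants with at least half of their CGM readings.

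**The concern.** The criteria select participants after randomisation and in one arm only. Poor adherence or a reading below 54 mg/dL can occur just as well in a control participant, who is not removed for it. Once a drug-arm participant has left, the pump-period contrasts (Objectives 1, 3 and 4) set a filtered arm against an unfiltered one, and randomisation no longer protects them. Replacement can bring the drug arm back to 20 completers, but all 20 will have passed the run-in; it restores the number and not the comparison.

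These contrasts are the trial's main evidence on adding the drug to Basal-IQ and Control-IQ. Pump-period CGM that was never recorded cannot be recovered at analysis, so the matter has to be settled in the protocol.

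**Working it through.** **1. The plan's own figure.** Section 15.2 gives 20 per arm at 90% power and alpha 0.01, from an effect size above 0.7 that the drug is assumed to double. With d = 2 x 0.7 = 1.4, two-sided, the noncentral-t formula needs 17 per arm; 20 per arm gives 95.1% power. With d = 0.7 it needs 63 per arm. Exactly 20 is not reproduced, because the d used is not stated. The present point does not depend on it; d = 1.4 serves below only to price the fix.

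**2. CGM held by a participant who fails.** The pump periods last 4 + 2 = 6 weeks. If the run-in counts toward the study period (which 15.1 does not define), coverage is 1/7 = 14% to 2/8 = 25%. If only pump weeks count, it is 0/6 = 0%. Both are below 50%, so the participant is excluded on either reading.

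**3. Chance that it happens.** The documents give no failure rate. If each of 20 has an assumed probability p of failing, P(at least one) = 1 - (1 - p)^20:

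| p | P(at least one) |
|---|---|
| 2% | 33% |
| 5% | 64% |
| 10% | 88% |

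**4. Shift in time in range (TIR).** Let f be the share failing and D the mean of those who pass minus the mean of those who fail. The full-arm mean is (passers' mean) - f x D, so using passers only shifts the arm by f x D. With f = 2/20 = 0.10 and an assumed D of -10 to +10 points, the shift is -1 to +1 point. With D of 15 points (the post-randomisation SD in the sensor-augmented-pump arm of Table 1) it is 0.10 x 15 = 1.5 points for two failures and 0.05 x 15 = 0.75 for one. Under no drug effect, two failures differing by one SD raise a nominal 0.05 error to about 0.06, and four to about 0.09.

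**5. Shift in time below 70 mg/dL** (first secondary in the hierarchy). Simulation with 2,000,000 draws, no drug effect and 10% of the drug arm removed. Run-in values are lognormal with mean 3.59 and SD 3.39, pump-period values lognormal with 1.59 and 1.15 (both from the closed-loop arm of Table 1). The log-scale correlation r is an assumption. Points x 14.4 = min/day.

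| r | Highest run-in values fail | Failure proportional to run-in value |
|---|---|---|
| 0.4 | -5.9% (1.4 min/day) | -2.5% (0.6 min/day) |
| 0.6 | -9.6% (2.2 min/day) | -4.0% (0.9 min/day) |
| 0.8 | -13.7% (3.1 min/day) | -5.6% (1.3 min/day) |

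The documents give no Basal-IQ distribution, so this covers Control-IQ only.

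**6. Does baseline adjustment repair it?** In the null simulation, adjusting for run-in time below 70 leaves a bias of about 1% or less. But the drug arm's run-in CGM is recorded on drug, so it is a post-treatment covariate. With nobody removed and a true 20% reduction in both periods, the adjusted estimate shrinks to about 9-15%. Nor does the adjustment address selection on ketones, infection, hypotension or adherence.

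**The case against.** The strongest reply is that these are safety criteria for an unapproved use, that few will fail, and that the bias is small. Much of this stands. Extra run-in time is allowed, the ketone criterion can be read as met by two successive acceptable readings, and 10.5 lets the drug restart once ketones fall below 0.6 mmol/L, so some failures may only be delays. The illustrated TIR shift of about 1 point is small beside the 11-point device difference in Table 1. The 6-14% figure needs every failure to come from the top of one ranking, whereas the actual criteria are mixed. Section 15.1 also describes the work as a pilot, meant partly to gauge effect sizes. None of this makes the comparison ITT, and the safety aim does not require data collection to end.

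A second reply is that the mixed model in 15.1 handles missing data. It cannot supply a pump-period outcome for someone whom the 50% rule has already excluded.

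A reader might also infer three stronger things that the documents do not support:
- That the results will favour the drug. This is the likely direction for unadjusted time below 70 mg/dL; for TIR, the primary outcome, the direction is uncertain.
- That 15.2 contradicts the design by placing most dropout before randomisation. That sentence reports experience in earlier studies, not this trial's sequence.
- That all replacement of dropouts is at fault. Only replacement of run-in failures bears on this point.

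**Conclusion.** The point holds in conditional form. From the first run-in failure, Objectives 1, 3 and 4 are comparisons of passers with unselected controls and not the ITT analysis that 15.1 declares. This follows from the text and needs no assumption about the failure rate. Its numerical importance is unknown: the failure probabilities, the TIR difference and the run-in correlation above are all assumed, and if nobody fails there is no bias.

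Reading the defect as one that invalidates the trial goes too far while the failure rate is unsourced and the illustrated effect on the primary outcome is about 1 point. Objective 2 uses the run-in CGM itself, and 15.1 reports safety for all enrolled; neither depends on pump-period data. It is a design weakness that is cheap to remove now and cannot be repaired later.

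**What to change.** Amend 9.1.1 so that failing a criterion stops or withholds Empagliflozin but does not end participation. Keep every safety criterion and the physician's option of more time. Section 10.5 already works this way: at ketones of 0.6 mmol/L or above, "participants will be advised to stop the drug and then recheck ketones in 3-4 hours", with a restart possible afterwards. The participant then follows the assigned pump sequence off drug, with study CGM to the planned end (CGM only if 13.9.1 rules out the device), and is analysed as randomised in Objectives 1, 3 and 4.

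State that run-in failures are not dropouts to be replaced under Chapter 5, and that discretion under 14.2 does not remove them from the analysis. Replacement of other dropouts can stay: barring it would, at the plan's 20% attrition (16 per arm), lower power at d = 1.4 and alpha 0.01 from 95% to 88%. Report the number failing each criterion, and label any analysis restricted to passers as supplementary.

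**Cost.** A short amendment, up to six already planned device weeks per failure, and dilution. With 20 per arm, two-sided tests and 10% failing with no drug effect, the mean effect is 0.9 x 1.4 = 1.26. Power falls from 99% to 97% at alpha 0.05, and from 95% to 87-89% at alpha 0.01 (lower figure: simulation with 2 of 20 at zero effect; upper: noncentral t). If doubling means that the drug adds a further 0.7, power at alpha 0.05 is 58% with no failures and about 49% at 10%. Event rates on drug plus closed loop would still come only from those who stay on drug.
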